## Study activities

- **Eligibility Criteria**

- Inclusion Criteria:
  - ✓ aged between 30 and 65 years old;
  - ✓ no significant skin lesions or inflammation on the facial skin;
  - ✓ willing and able to comply with study requirements, instructions, and restrictions;
  - ✓ signed informed consent form.
- Exclusion Criteria:
  - ✓ underwent facial active treatment, such as using laser, intense pulsed light, radiofrequency skin tightening, ultrasound skin tightening, botulinum toxin, or dermal fillers injection, within the previous six months;
  - ✓ have chronic skin diseases such as atopic dermatitis, psoriasis, chronic urticaria, vitiligo, rosacea, or keloid;
  - ✓ pregnant or breastfeeding;
  - ✓ suffered from acute illnesses or infections requiring treatment within 14 days before entering the study;
  - ✓ have had serious illnesses (such as heart disease, lung disease, brain disease, or liver disease) within the previous three months;

- ✓ allergic to Lidocaine or Prilocaine used in topical anesthetic cream or suffer from methemoglobinemia;
- ✓ used any skin medication on the face within 30 days before the trial, deemed by the principal investigator to affect the study results;
- ✓ deemed unsuitable for the study by the principal investigator.

- **Limitations and Cooperation Requirements for Study Participants**

- Limitations for study participants during the trial
  - ✓ Participants are not allowed to undergo other chemical peels, beauty injections or phototherapy around the eyes during the trial.
  - ✓ Participants should avoid sun exposure or the use of tanning machines on their face during the trial.
  - ✓ Participants should maintain their original skincare routine during the trial and avoid using new facial skin products or topical/ingested whitening agents that claim to have whitening, spot-fading, or wrinkle-fighting effects.
- Cooperation requirements for study participants during the trial
  - ✓ Participants should use umbrellas or wear hats to protect themselves from the sun when going outside on days with high UV index.
  - ✓ Participants can clean their faces as usual, but they must maintain a similar cleaning pattern every day.
  - ✓ Participants can use facial moisturizers, sunscreens, makeup, and makeup removers as usual, but they must maintain a similar pattern every day.
- Consequences of failure to comply with trial limitations or cooperation requirements
  - ✓ If participants use the above limited items or fail to cooperate with the above requirements during the trial, they should inform the researchers actively. The principal investigator will assess whether the products or treatments used by the participants have any impact on the trial's test results and safety, as well as the feasibility of the participants continuing to participate in the trial.

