## Study objectives and endpoints

- **Objectives:** The objective of this study is to evaluate the treatment design, therapeutic effects and safety of the 1927 nm laser for the rejuvenation of the skin around the eyes.
- **Primary endpoint**
  1. Change from baseline in texture score at visit 4 (follow-up session)
- **Secondary endpoints**
  1. Change from baseline in color measurements (L\*) at visit 4 (follow-up session)
  2. Change from baseline in pigmentation score at visit 4 (follow-up session)
  3. Change from baseline in pores' index at visit 4 (follow-up session)
  4. Change from baseline in physician assessment of Global Aesthetic Improvement Score (GAIS), at visit 4 (follow-up session)
  5. Change from baseline in patient assessment of Global Aesthetic Improvement Score (GAIS), at visit 4 (follow-up session)
  6. Change from baseline in texture score at visit 2
  7. Change from baseline in color measurements (L\*) at visit 2
  8. Change from baseline in pigmentation score at visit 2
  9. Change from baseline in pores' index at visit 2
  10. Change from baseline in physician assessment of Global Aesthetic Improvement Score (GAIS), at visit 2
  11. Change from baseline in patient assessment of Global Aesthetic Improvement Score (GAIS), at visit 2
  12. Change from baseline in texture score at visit 3
  13. Change from baseline in color measurements (L\*) at visit 3
  14. Change from baseline in pigmentation score at visit 3
  15. Change from baseline in pores' index at visit 3
  16. Change from baseline in physician assessment of Global Aesthetic

- Improvement Score (GAIS), at visit 3
- 17. Change from baseline in patient assessment of Global Aesthetic Improvement Score (GAIS), at visit 3
- 18. Adverse reaction after each treatment
- 19. Visual Analogue Scale (VAS) during treatment
- 20. Change from baseline in self-reported satisfaction with the skin around the eyes

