## **Investigational plan**

- **Study Design**

This is an open-label, single center clinical study to evaluate the efficacy of periorbital rejuvenation with a 1927 nm diode laser treatment. The trial administrator will assign the subjects into different treatment groups (Group A: 2-week interval between treatments, or Group B: 4-week interval between treatments) .

- **Randomization**

This study is designed as a randomized clinical trial. The randomization of subjects will be generated by computer algorithm prior to the start of the trial. The trial administrator will assign the subjects into different treatment groups (Group A: 2-week interval between treatments, or Group B: 4-week interval between treatments) based on the order of enrollment and the corresponding randomization code.

- **Screening**

Upon obtaining the signed informed consent form, the trial staff will record the subjects' basic information, medical and surgical history, medication history, and Fitzpatrick skin type. Women will undergo pregnancy testing, and inclusion and exclusion criteria will be reviewed.

- **Treatment Visits**

- Visit 1

Before the first treatment, a camera photograph and Antera 3D assessment will be performed, and the subjects will complete a self-assessment questionnaire for skin conditions. EMLA Cream 5% will be applied topically for 20 minutes. Ocular laser shields will then be placed over the eyes following the application of Alcaine Ophthalmic Solution 0.5%. Clear + Brilliant™ Permea device periorbital treatment will then be performed. After the treatment, the subjects will complete a visual analog scale (VAS) for pain and use moisturizing skincare products.

- Visit 2

Before the second treatment, a camera photograph and Antera 3D assessment will be performed, and the subjects will complete a self-assessment questionnaire for skin conditions, the Global Aesthetic Improvement Scale (GAIS) for overall aesthetic improvements, and a treatment safety questionnaire. EMLA Cream 5% will be applied topically for 20 minutes. Ocular laser shields will then be placed over the eyes following the application of Alcaine Ophthalmic Solution 0.5%. Clear + Brilliant™ Permea device periorbital treatment will then be performed. After the treatment, the subjects will use moisturizing skincare products.
- Visit 3

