## **Data Collection, Processing, Evaluation, and Statistical Analysis**

### **Methods**

- **Data Confidentiality**

To maintain data confidentiality, data will be entered into a computer using a numbering system, and the data will be stored on an encrypted computer in the lead investigator's institution. The study lead investigator and research team members have a duty of confidentiality regarding information about the subjects and follow the rule that data cannot be taken out of the hospital.

- **Protection of Subjects' Privacy**

The research team will use a study code to represent the identity of the subjects, and only the lead investigator and relevant research team members will know the link between the code and the name. If the trial/research results are published, the subjects' identities will still be kept confidential.

- **Statistical analysis**

- For the analysis of numerical data, we will use either an independent t-test or Mann-Whitney U test to compare differences between the two groups. Additionally, a paired t-test or Wilcoxon signed-rank test will be used to compare differences between before and after treatment.
- For categorical data, we will present the data in the form of frequency and contingency tables. To determine if there are significant differences in rates between the two groups, we will use either the chi-square test or Fisher's exact test.
- All reported P-values will be from two-sided tests, and statistical significance will be determined at a threshold of  $P < 0.05$ .

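### Entry does not require any visible periorbital texture change, so subjects with less room to improve can dilute the texture effect and make a null A-versus-B result hard to read

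*Combined protocol and SAP*

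**What the plan says.** Under Study activities, Eligibility Criteria, there are four inclusion criteria: "aged between 30 and 65 years old", "no significant skin lesions or inflammation on the facial skin", willingness to comply, and consent. The exclusions cover recent facial procedures, chronic skin disease, pregnancy or breastfeeding, recent illness, allergy to the anaesthetic cream or methaemoglobinaemia, facial skin medication, and anyone "deemed unsuitable for the study by the principal investigator". None concerns the degree of periorbital ageing.

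Screening, under Investigational plan, records history, medication and Fitzpatrick type, adds a pregnancy test for women, and reviews the criteria. It includes no severity grade. Texture is first measured at Visit 1: "Before the first treatment, a camera photograph and Antera 3D assessment will be performed". That reading is not an entry threshold.

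The study is meant to "evaluate the efficacy of periorbital rejuvenation with a 1927 nm diode laser treatment". Its primary endpoint is the Visit 4 change in texture score, and physician and patient GAIS rate improvement at Visits 2 to 4. For numerical data the statistical section says "we will use either an independent t-test or Mann-Whitney U test to compare differences between the two groups", with a paired t-test or Wilcoxon signed-rank test for before versus after. It names no baseline covariate and no analysis by baseline severity.

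**The concern.** The treatment is meant to rejuvenate, and the primary measure is change in texture, yet nothing at entry ensures that there is texture to change. A 30-year-old with smooth, even skin meets every listed criterion, is treated three times and counts in the texture and GAIS analyses.

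Two things are at stake. The first is sensitivity: such subjects may add variability to both planned comparisons while contributing less of the effect. The second is interpretation. If Groups A and B do not differ, the two intervals may be equivalent in practice, or too many subjects may have had little to improve. The plan contains nothing that would separate these explanations.

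**Working it through.** **Inputs from the documents.** Two-sided significance level 0.05; the Visit 4 change in texture score as endpoint; the tests named above. There is no stated sample size, power, effect size, SD or texture range, so there is no figure of the plan's own to reproduce.

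**Assumptions.** A share f of subjects is of low severity and carries a fraction k of the A-versus-B difference; the rest carry all of it. The SD of change is the same in both kinds of subject, and the spread between their mean changes is ignored. The reference is a hypothetical trial with 80% power at f = 0.

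**A versus B.** The difference shrinks by c = 1 − f(1 − k). The required number rises by 1/c². Power becomes Φ(2.80c − 1.96), where 2.80 = 1.96 + 0.84.

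| f | k | c | 1/c² | Power |
|---|---|---|---|---|
| 20% | 0.5 | 0.90 | 1.23 | Φ(0.56) = 71% |
| 30% | 0.5 | 0.85 | 1.38 | Φ(0.42) = 66% |
| 20% | 0 | 0.80 | 1.56 | Φ(0.28) = 61% |
| 30% | 0 | 0.70 | 2.04 | Φ(0.00) = 50% |

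For scale, a standardised difference of 0.5 needs 63 per arm at f = 0. With k = 0 this becomes 99 per arm at f = 20% and 129 at f = 30%.

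**Sensitivity to the equal-SD assumption.** Keep k = 0, give low-severity subjects half the SD of change, and let the mean improvement in the others be 0.5 SD. The variance, in units of the improvable subjects' variance, is (1 − f) + 0.25f + 0.25f(1 − f):

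- f = 20%: variance 0.89, factor 0.89/0.64 = 1.39, power 66%.
- f = 30%: variance 0.8275, factor 0.8275/0.49 = 1.69, power 58%.

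Both lie between the half-effect and no-effect rows above.

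**Before-after change.** Take a standardised change of d = 0.5 in improvable subjects and none in the rest. Then the mean is d(1 − f) and the variance is 1 + f(1 − f)d². With n = 32, power is 81% at f = 0:

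- f = 20%: mean 0.40, SD √1.04 = 1.020, power Φ(0.40 × √32/1.020 − 1.96) = 60%.
- f = 30%: mean 0.35, SD √1.0525 = 1.026, power Φ(0.35 × √32/1.026 − 1.96) = 49%.

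**Why the cut should not use the Visit 1 reading.** Selecting the upper half on a single reading with reliability r shifts the later mean by (1 − r) × 0.798 SD without any treatment effect. That is 0.08 SD at r = 0.9 and 0.16 SD at r = 0.8; both reliabilities are assumed. With no untreated arm, this would pass for improvement.

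**The case against.** The strongest reply is that the harm is assumed. The documents give no lower bound for texture, no baseline distribution and no relation between severity and response. The description of the Antera 3D, which quantifies wrinkle depth and width and overall roughness, suggests a continuous measure. A reader might infer that smooth-skinned subjects cannot improve at all; the documents do not show such a floor, so less room to improve is as far as one can go. For the same reason the k = 0 rows are an upper case, and the half-effect rows belong beside them. If f is small, little is lost.

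A reader might also infer that the A-versus-B comparison is biased. It is not: randomisation is expected to spread low-severity subjects evenly, and the before-after mean remains a valid average for whoever enrols. Nor can one say that planned power is lost, since none is stated. And the lesion criterion should not be read as demanding skin free of ageing; the issue is an omission.

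The investigator's discretion to exclude is open-ended and could be used for a subject with nothing to treat, and the age minimum of 30 may lower f. Both points stand in part, but neither sets a standard that a reader could check.

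Finally, broad entry can be deliberate. The objective takes in "therapeutic effects and safety of the 1927 nm laser for the rejuvenation of the skin around the eyes" as well as treatment design, and L*, pigmentation and pores are secondary endpoints. The documents give no such rationale for the entry criteria, but the point limits how strongly a restriction should be urged.

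**Conclusion.** The concern holds as a matter of sensitivity and interpretation. The criteria set no minimum periorbital texture change, and no other section supplies one. Subjects with less to gain can enter, which can dilute both the group difference and the before-after change and leaves a null A-versus-B result ambiguous.

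The size cannot be derived from the documents. The figures above rest on an assumed f of 20-30%, on the assumed fraction of the effect that low-severity subjects carry, and on a hypothetical 80% reference power. This is an optional design improvement, held with medium-to-low confidence.

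**What to change.** Add one inclusion criterion under Eligibility Criteria: at least mild visible periorbital fine lines or uneven texture on a named, fixed grading scale, rated by the investigator at the criteria review before the group is known. The protocol must name the scale. Nothing in the documents links a visual grade to the Antera score, so how far the criterion lowers f on the primary measure is uncertain. Do not use the Visit 1 Antera reading as the cut.

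If broad entry is intended, say so, prespecify baseline texture as a covariate, and report change by baseline severity. That would help in reading a null result, but it would not restore an effect diluted by enrolment.

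The cost is one rating at a review already planned, with no new visit, staff or instrument. Recruitment would be slightly slower, and the result would apply to people with at least mild periorbital texture change. People whose only concern is pigment or pores would be excluded, although both are secondary endpoints.

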## **Adverse Reactions and Management in Clinical Settings**

- Allergic contact dermatitis caused by topical anesthetic cream has an incidence rate of less than 0.1%, which may result in skin redness, swelling, mild burning or itching. Topical steroid cream can be used for treatment.
- This device may cause local transient pain (lasting about one to several

hours) and redness and swelling (lasting about one to two days). Most of these side effects will disappear on their own. If the symptoms persist, symptom relief medication such as oral pain relievers like acetaminophen or non-steroidal anti-inflammatory drugs can be used.

- Small scabs the size of a needle tip may appear, which will fall off on their own within a week.
- If inflammation and pigmentation occur due to the constitution or sun exposure, topical or oral whitening products can be used for treatment for 1-3 months.

## **Data Collection, Processing, Evaluation, and Statistical Analysis**

### **Methods**

- **Data Confidentiality**

To maintain data confidentiality, data will be entered into a computer using a numbering system, and the data will be stored on an encrypted computer in the lead investigator's institution. The study lead investigator and research team members have a duty of confidentiality regarding information about the subjects and follow the rule that data cannot be taken out of the hospital.

- **Protection of Subjects' Privacy**

The research team will use a study code to represent the identity of the subjects, and only the lead investigator and relevant research team members will know the link between the code and the name. If the trial/research results are published, the subjects' identities will still be kept confidential.

- **Statistical analysis**

- For the analysis of numerical data, we will use either an independent t-test or Mann-Whitney U test to compare differences between the two groups. Additionally, a paired t-test or Wilcoxon signed-rank test will be used to compare differences between before and after treatment.
- For categorical data, we will present the data in the form of frequency and contingency tables. To determine if there are significant differences in rates between the two groups, we will use either the chi-square test or Fisher's exact test.
- All reported P-values will be from two-sided tests, and statistical significance will be determined at a threshold of  $P < 0.05$ .

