Before the third treatment, a camera photograph and Antera 3D assessment will be performed, and the subjects will complete a self-assessment questionnaire for skin conditions, GAIS for overall aesthetic improvements, and a treatment safety questionnaire. EMLA Cream 5% will be applied topically for 20 minutes. Ocular laser shields will then be placed over the eyes following the application of Alcaine Ophthalmic Solution 0.5%. Clear + Brilliant™ Permea device periorbital treatment will then be performed. After the treatment, the subjects will use moisturizing skincare products.
- Visit 4

Four weeks after the third treatment, a follow-up assessment will be performed, including a camera photograph and Antera 3D assessment, self-assessment questionnaire for skin conditions, GAIS for overall aesthetic improvements, and a treatment safety questionnaire.
- **Time of Each Visit**

Each visit lasts approximately 40 minutes, including 20-minute topical anesthesia, 15-minute laser treatment, and 5-minute photography.
- **Laser treatment**

Solta CLEAR+BRILLIANT Laser System, featuring a 1927 nm diode laser with 5 mJ energy, a treatment spot of 140 µm, a treatment depth of 170 µm, and a treatment coverage of approximately 5% per energy level after four rounds of treatment using the patented Intelligent Optical Tracking® System (IOTs). We will perform laser treatment on the periorbital area.
- **Imaging Records**

Each visit will include:

  - Camera photograph: One photograph of periorbital area in half-face position (from the eyebrows to the lower nose).

- Antera 3D photography: Two photographs of both sides of the periorbital area (5.6 x 5.6 cm), along with L\*, texture, pigmentation, and pore indices. A total of eight photographs will be taken.
- **Other Study Procedures**
  - Basic information survey, including date of birth, gender, Fitzpatrick skin type, and medication history.
  - Height and weight
  - Medical and surgical history, including a survey of past and current illnesses, allergies, and surgical history.
  - Medication history, concurrent use of medications, or related aesthetic treatments
  - Pregnancy test: urine pregnancy test (only performed on women before menopause).
  - Self-assessment questionnaire for skin condition
  - Global aesthetic improvement scale (GAIS) from subjects and investigator
  - Treatment safety questionnaire
  - Pain VAS (Pain Visual Analogue Scale)
  - Antera 3D camera
 

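### The randomised A-versus-B comparison of texture uses no covariate although baseline texture is collected; adjusting for it usually gains precision and needs no new data

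*Combined protocol and SAP*

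**What the plan says.** The primary endpoint (Study objectives and endpoints) is "Change from baseline in texture score at visit 4 (follow-up session"). Under Randomization the protocol states "This study is designed as a randomized clinical trial", with Group A treated at 2-week and Group B at 4-week intervals. That is the only randomised contrast.

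For numerical data, the Statistical analysis section says "we will use either an independent t-test or Mann-Whitney U test to compare differences between the two groups". It adds that "a paired t-test or Wilcoxon signed-rank test will be used to compare differences between before and after treatment". "All reported P-values will be from two-sided tests", with significance at P < 0.05 for both kinds of test. No covariate, ANCOVA, regression or mixed model appears anywhere.

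Baseline texture is planned. At Visit 1, "Before the first treatment, a camera photograph and Antera 3D assessment will be performed"; the visit schedule repeats the Antera 3D assessment at all four visits, and Imaging Records lists texture among its outputs. Imaging covers both sides of the face: "Two photographs of both sides of the periorbital area (5.6 x 5.6 cm").

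**The concern.** A change score subtracts the whole baseline value, as if the slope of Visit 4 on baseline were 1. When the true slope is smaller, as regression to the mean usually makes it, subtraction over-corrects, and part of any chance baseline imbalance stays in the estimate. ANCOVA estimates the slope instead. Without it, the trial's one randomised contrast may be reported with a wider interval than the collected data allow.

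Two related points bear on how that contrast is reported:

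- Both groups receive the laser and neither is an untreated control. The before-after tests therefore cannot say which interval is better, nor separate the laser from time or aftercare. The plan gives them the same significance threshold and does not say which test decides the primary endpoint.
- Both sides are imaged, but no rule says how they form one value per subject. The plan does not say that sides will be analysed separately, so this is a conditional risk only.

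**Working it through.** **Inputs from the document.** Two randomised groups; texture change at Visit 4 as primary endpoint; texture measured at Visit 1 before treatment; two-sided 0.05. There is no stated precision or power figure to reproduce.

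**Inputs assumed, because the document gives none.** r = correlation of baseline and Visit 4 texture, 0.5 to 0.9; k = Visit 4 SD divided by baseline SD, at 0.8, 1 and 1.25; N = total subjects, 20 or 40, allocated 1:1; normal data with a common slope. The comparator is the t-test on change, since the primary endpoint is a change score.

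**Formula.** With baseline SD set to 1, the per-subject variance is:

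- change score: 1 + k² − 2rk
- ANCOVA: k²(1 − r²), multiplied by 1 + 1/(N − 4) for estimating the slope

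Ratio = k²(1 − r²)/(1 + k² − 2rk) × (1 + 1/(N − 4)). With k = 1 and large N this is (1 + r)/2.

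Example: k = 1, r = 0.5, N = 40 gives 0.75 × (1 + 1/36) = 0.771.

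**Variance ratio, ANCOVA to change score (below 1 favours ANCOVA)**

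| k | Subjects per arm | r = 0.5 | r = 0.7 | r = 0.8 | r = 0.9 |
|---|---|---|---|---|---|
| 1 | large | 0.75 | 0.85 | 0.90 | 0.95 |
| 1 | 20 | 0.771 | 0.874 | 0.925 | 0.976 |
| 1 | 10 | 0.797 | 0.903 | 0.956 | 1.009 |
| 0.8 | 20 | 0.587 | 0.645 | 0.658 | not run |
| 1.25 | 20 | 0.918 | 1.008 | 1.028 | not run |

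**In other units (k = 1, 20 per arm, r = 0.5, 0.7, 0.8, 0.9).** CI width ratios are 0.879, 0.936, 0.963 and 0.989, so intervals are about 12%, 6%, 4% and 1% narrower. The unadjusted test would need 20/ratio − 20 = 5.9, 2.9, 1.6 and 0.5 more subjects per arm to match.

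**Limit on the loss.** (1 + k² − 2rk) − k²(1 − r²) = (1 − rk)², which is never negative. Under this model the only cost of ANCOVA is the slope term: at most 1/36 = 2.8% of variance at N = 40 and 1/16 = 6.3% at N = 20. The k = 1.25, r = 0.8 cell has rk = 1 and so sits exactly at that limit.

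**Simulation check (20,000 trials per setting, k = 1).** Over N = 12 to 40 and r = 0.3 to 0.9, type I error was 4.7% to 5.2% for both methods. Where the change-score test had about 80% power at N = 40, ANCOVA had 89%, 85% and 81% at r = 0.5, 0.7 and 0.9. The least favourable setting was N = 12 with r = 0.9: power 77% against 80%.

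**Sides, only if entered as separate observations.** With a correlation rho between the two sides' changes, the true variance is (1 + rho) times what the t-test assumes. The large-sample type I error is then 2(1 − Φ(1.96/√(1 + rho))) = 7.4%, 8.6%, 11.0% and 15.5% at rho = 0.2, 0.3, 0.5 and 0.9.

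**The case against.** The planned test is not wrong. A t-test on change between randomised groups is standard, unbiased, and holds its type I error in the simulation. Baseline is not ignored either, because it is already subtracted; ANCOVA only alters its weight. With no sample size, SD or correlation in the document, the benefit cannot be fixed, and at high r or with a larger Visit 4 SD it is small or absent. Every figure compares ANCOVA with the t-test and none with the Mann-Whitney test, so a gain over that test on skewed data is not shown. The plan never says that the before-after tests decide the A-versus-B question, nor that sides are separate observations.

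Most of this stands as a limit on size. The point concerns efficiency, its magnitude is conditional, and no comparison with Mann-Whitney has been made. It does not remove the case for the change, because the trade is lopsided: at 20 per arm the loss cannot exceed about 3% of variance under the stated model, while the scenarios show reductions of up to 41%. The before-after and two-sides points are secondary; the case for ANCOVA does not depend on them.

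**Conclusion.** The concern holds as a matter of precision, not validity. The A-versus-B comparison is planned without a covariate although the most useful one is already scheduled for every subject. At 20 per arm with equal SDs the variance reduction is 23% at r = 0.5, falling to 2.4% at r = 0.9. Across the SD ratios examined, the result runs from a 41% reduction to a 3% increase. At 10 per arm with equal SDs it runs from a 20% reduction to a 1% increase. All of this assumes 1:1 allocation, normal data and a common slope, with r, k and N supplied by assumption.

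The change should be made, and prespecified before data are seen. It does not address the different Visit 4 timing in the two groups (Week 8 in A, Week 12 in B), which is a separate matter.

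**What to change.** In the Statistical analysis section:

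- Analyse the A-versus-B comparison of Visit 4 texture by ANCOVA with group and Visit 1 texture in the model, using the left-right mean as the single value per subject at each visit. Report the adjusted difference with its 95% CI.
- Use the same model for L*, pigmentation and pores, each with its own Visit 1 value.
- Keep the Mann-Whitney test on change as a sensitivity analysis.
- Report before-after changes as within-group estimates with CIs, not as the test that settles the randomised question. If before-after change is also meant as a main result, say so and label it uncontrolled.

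The cost is wording and one degree of freedom; there are no new data or procedures. With a very small sample and high r, or a larger Visit 4 SD, there may be no gain. The sponsor must also accept A versus B as the contrast that answers the randomised question.

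### The tests named for Visit 4 texture change default to subjects with a Visit 4 reading, which can bias the A-versus-B comparison if response-related dropout differs between arms

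*Combined protocol and SAP*

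**What the plan says.** The primary endpoint, under Study objectives and endpoints, is "Change from baseline in texture score at visit 4 (follow-up session". The matching Visit 2 and Visit 3 changes are separate secondary endpoints, numbers 6 and 12: "Change from baseline in texture score at visit 2" and "Change from baseline in texture score at visit 3".

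Subjects are randomised to "Group A: 2-week interval between treatments, or Group B: 4-week interval between treatments". On Visit 4 the Investigational plan says: "Four weeks after the third treatment, a follow-up assessment will be performed". The schedule table puts that visit at Week 8 in Group A and Week 12 in Group B, and it lists the Antera 3D assessment, which yields texture, at all four visits.

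For numerical data the Statistical analysis section gives two rules. Between groups, "we will use either an independent t-test or Mann-Whitney U test to compare differences between the two groups". Within subjects, "a paired t-test or Wilcoxon signed-rank test will be used to compare differences between before and after treatment". Tests are two-sided at P < 0.05. The section names no analysis set, missing-data method, repeated-measures model or sensitivity analysis. No dropout rate or sample size appears anywhere.

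**The concern.** A change score at Visit 4 needs a Visit 1 and a Visit 4 value. Unless values are imputed, and no imputation is mentioned, a subject without Visit 4 is left out of the test on that endpoint. Any Visit 2 or Visit 3 reading from that subject then adds nothing to the Visit 4 comparison, although it may well predict the missing value.

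Randomisation protects the comparison of everyone randomised. It does not protect the comparison of those who stay. If poor responders are more likely to leave, and more of them leave one arm, the arm that loses more looks better than it is.

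Loss of this kind is plausible here. Subjects rate their own skin at Visits 2 and 3, treatment is open-label, and the participant restrictions last 12 weeks in one arm and 8 in the other. After a breach of those restrictions the investigator assesses whether the subject can continue, and no rule says what then happens to that subject's data.

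**Working it through.** The plan gives no sample size, SD or dropout figure, so there is nothing of its own to reproduce. The check has four steps.

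**1. Where the arms differ in time (schedule table).**

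| | Visit 1 to 2 | Visit 2 to 3 | Visit 3 to 4 | Total |
|---|---|---|---|---|
| Group A (Weeks 0, 2, 4, 8) | 2 | 2 | 4 | 8 |
| Group B (Weeks 0, 4, 8, 12) | 4 | 4 | 4 | 12 |
| B minus A | 2 | 2 | 0 | 4 |

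Group B is followed 12/8 = 1.5 times as long, but the whole excess falls before Visit 3.

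**2. When completers mislead.** In an arm with dropout proportion d, mean of all = (1 − d) × completer mean + d × dropout mean. Hence completer mean − mean of all = d × g, where g = completer mean − dropout mean. The bias in B minus A is therefore d_B × g_B − d_A × g_A.
- It is zero if g = 0 in both arms, however unequal the dropout.
- It is zero if d and g are the same in both arms.
- Otherwise it is generally not zero.

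**3. Illustrative size (all inputs assumed).** Changes at Visits 2, 3 and 4 have SD 1 and pairwise correlation 0.6. There is no true A–B difference, and improvement is coded as a fall in score. Loss occurs after Visit 3. It is either unrelated to outcome or logistic in the Visit 3 or the Visit 4 change, with log-odds slope 0.7 or 1.5 per SD and worse responders leaving more often. Two estimates are compared: the difference in completer means, and a likelihood-type estimate that also uses Visits 2 and 3. Each setting uses 1,000,000 subjects per arm, so simulation error is about √(2/1,000,000) = 0.0014. Entries are bias in B minus A, in SD of change; negative favours B.

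| Dropout A v B | Slope | Unrelated: completers | On Visit 3: completers | On Visit 3: using Visits 2–3 | On Visit 4: completers | On Visit 4: using Visits 2–3 |
|---|---|---|---|---|---|---|
| 5% v 15% | 0.7 | 0.000 | −0.040 | −0.001 | −0.064 | −0.036 |
| 5% v 25% | 0.7 | 0.001 | −0.075 | 0.001 | −0.128 | −0.074 |
| 10% v 20% | 0.7 | −0.001 | −0.036 | 0.002 | −0.065 | −0.037 |
| 10% v 30% | 0.7 | 0.000 | −0.071 | 0.003 | −0.126 | −0.073 |
| 5% v 15% | 1.5 | 0.001 | −0.068 | −0.002 | −0.112 | −0.068 |
| 5% v 25% | 1.5 | 0.003 | −0.129 | −0.001 | −0.213 | −0.132 |
| 10% v 20% | 1.5 | 0.002 | −0.062 | 0.000 | −0.102 | −0.063 |
| 10% v 30% | 1.5 | 0.000 | −0.124 | 0.000 | −0.207 | −0.131 |

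With equal dropout by the same mechanism (5% v 5%, 10% v 10%) every entry is within 0.003 of zero.

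**4. Effect on the test.** This takes 5% v 25% dropout, slope 1.5, and 8,000 trials per setting at nominal 0.05.

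| Per arm (assumed) | Unrelated | On Visit 3 | On Visit 4 |
|---|---|---|---|
| 10 | 0.054 | 0.054 | 0.070 |
| 20 | 0.050 | 0.063 | 0.096 |
| 50 | 0.050 | 0.090 | 0.176 |

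Hand check at 20 per arm: completers number 19 and 15, so the standard error is √(1/19 + 1/15) = 0.345 and the bias is 0.129/0.345 = 0.37 standard errors. The normal approximation gives Φ(−1.96 + 0.37) + Φ(−1.96 − 0.37) ≈ 0.056 + 0.010 = 0.066, close to the simulated 0.063.

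**The case against.** The strongest objection is about timing. Visit 4 comes four weeks after Visit 3 in both arms, so the illustration puts its imbalance in the one interval where the schedules are alike. Extra loss caused by Group B's longer intervals would come earlier. Those subjects have no Visit 3 reading, and anyone lost before Visit 2 has no post-baseline reading at all. This stands. The near-zero bias shown when Visits 2 and 3 are used depends on those readings being present, so the gain from the model would be smaller for earlier losses. It does not vanish, because the model still uses whatever Visit 1 and Visit 2 readings exist.

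The effect is also modest. The largest figures need a fivefold dropout imbalance and a steep slope, and with 10 to 20 per arm the test's error rate barely moves when loss depends on Visit 3. That stands too.

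Three stronger readings are tempting, and the documents support none of them:
- A reader might infer that the plan prescribes a completers-only analysis. It is silent; completers are only what the named tests use by default.
- A reader might infer that the Visit 2 and 3 readings are thrown away. They are analysed as secondary endpoints and are unused only for the Visit 4 comparison.
- A reader might infer that A versus B is the declared primary contrast. The endpoint names no contrast, and a before-after test is also planned. A versus B is, however, the randomised comparison.

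**Conclusion.** The point holds as a conditional risk and a gap that is cheap to close. A reader might go further and conclude that 12 v 8 weeks of follow-up biases the result. The documents do not support that: they give no dropout rate, no imbalance and no reasons for leaving, and unequal dropout unrelated to response gave bias of 0.003 SD or less, which is simulation noise.

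If loss depends on Visit 3 response and is 5–10% v 15–25%, the completer comparison is off by roughly 0.04 to 0.13 SD of change, in favour of the arm that loses more. If loss depends on the unseen Visit 4 value, the same approach gives 0.064 to 0.213 SD. Using the earlier visits reduces this to 0.036 to 0.132 SD but does not remove it. All these sizes rest on the assumed correlation, slopes, dropout rates and timing of loss. The change is worth making before the data are seen; it does not show the design to be unsound.

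**What to change.** For the A-versus-B difference in texture change at Visit 4, prespecify a mixed model for repeated measures on texture at Visits 1–4. Include group, visit as a category and group-by-visit, with unstructured covariance and a small-sample degrees-of-freedom correction such as Kenward-Roger. Include every randomised subject with any reading. With complete data this gives the same result as the t-test on change.

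Alongside it:
- Keep the t-test or Mann-Whitney test on completers as a sensitivity analysis.
- Report missing Visit 4 readings by arm.
- Add a simple sensitivity analysis for dropout that depends on unobserved outcomes, for example shifting the imputed Visit 4 values by a range of amounts in each arm. The model only reduces bias in that case, and it cannot correct response-related loss before any post-baseline reading.
- Use the same model for L*, pigmentation and pores.

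The cost is wording and slightly more analysis work, with no new visits, data or staff. The downside is reliance on a missing-at-random assumption, meaning that loss is explained by readings already observed. The unstructured covariance also has 4 × 5/2 = 10 parameters to estimate, which matters if the trial is small.
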